Efficacy Study of the LARA Wheelchair System for Subacute Stroke Patients

NCT 02830893

Standard Operating Procedures

February 28, 2018

Table of Content

- 1. Background and Population
- 2. Inclusion and Exclusion Criteria
- 3. Methods
- 4. Timeline of the Study
- 5. Table of Clinical Testing
- 6. List of Clinical Tests
- 7. Daily Study Procedures
- 8. Statistical Considerations

Background

We will recruit 44 individuals with an acute or subacute stroke (3 days to 30 days post stroke) to participate in this randomized controlled trial at UCI ARU and Rancho Los Amigos National Rehabilitation Center. These individuals will have an acute or subacute stroke with arm/ hand weakness defined as a score of less than 50 (out of 66) on the arm motor scale of the Fugl-Meyer Assessment.

Inclusion Criteria:

- 1. History of stroke affecting the arm, at least 3 days to 30 days prior to enrollment
- 2. Age 18 to 80 years of age
- 3. Upper extremity weakness, defined as a score of less than 50 (out of 66) on the arm motor scale of the Fugl-Meyer Assessment

Exclusion Criteria:

- 1. Moderate to severe pain in the stroke-affected upper extremity (score >6 on 10-point visual analog pain scale), at rest or increased when attempting to use LARA
- 2. Severe tone at the affected upper extremity (score >4 on the Ashworth Spasticity Scale)
- 3. Severe aphasia (score of 2 or higher on the NIH stroke scale question 9)
- 4. Deficits in vision, language, attention, or other cognitive functions severe enough to interfere with using LARA
- 5. Currently pregnant
- 6. Difficulty in understanding or complying with instructions given by the experimenter
- 7. Inability to perform the experimental task that will be studied

Methods:

The primary outcome measure will be the Upper Extremity Fugl-Meyer Score to assess motor impairment in the affected arm. Secondary outcome measures will be Box and Blocks Test, Modified Ashworth Scale of Spasticity to measure spasticity of the shoulder, elbow, wrist and hand, Visual Analog Pain scale to assess pain, NIH Stroke Scale, mini mental state exam to assess cognitive function and the Borg scale to access their perceived exertion levels. We will perform testing at three separate evaluations: At the initial baseline visit, 3-weeks post therapy or the day before discharge if sooner, and 3-month follow up. The end point of the study will be the 3-month after baseline evaluation.

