10	2			8	A: LARA or B: Tabletop exercise program
11	2			9	A: LARA or B: Tabletop exercise program
12	2			10	A: LARA or B: Tabletop exercise program
13	3			11	A: LARA or B: Tabletop exercise program
14	3			12	A: LARA or B: Tabletop exercise program
15	3			13	A: LARA or B: Tabletop exercise program
16	3			14	A: LARA or B: Tabletop exercise program
17	3			15	A: LARA or B: Tabletop exercise program
18	3	2	All clinical outcomes		
19	13	3	All clinical outcomes: Follow-up		

Table of Clinical Testing

	Screen	Evaluation #1	Evaluation #2	Evaluation #3
		(Baseline)	(Post therapy)	(3-month follow up)
Consent Form	Х			
HIPAA wavier form	Х			
Photography consent	X			
Medical History/ Health Status Questionnaire/ Rehab History overall	Х			
NIHSS	X	X	X	X
Box and Blocks Test		X	X	X
Mini Mental State Exam		X	X	Х
Modified Rankin Scale		X	X	Х
Motor sections of Fugl- Meyer	Х	Х	Х	Х
Action Research Arm Test		Х	Х	Х
Motor Activity Log		X	Х	X
10-meter walk		X	Х	X
Grip Strength		X	X	X
AROM & PROM at shoulder and elbow		Х	Х	Х
Geriatric Depression Scale		Х	Х	Х
Modified Ashworth Scale of Spasticity (Shoulder, Elbow, Wrist, Finger)	Х	Х	Х	Х
Visual Analog of Pain Scale	Х	Х	Х	Х
IMI	Х	X	X	X
Stipend	X	X	X	Х

List of Clinical Tests

- 1. Upper Extremity Fugl-Meyer Motor Score study primary outcome measure
- 2. Box and Blocks Test
- 3. Motor Activity Log
- 4. Action Research Arm Test
- 5. Active and passive range of motion at the shoulder and elbow
- 6. Modified Ashworth Spasticity Scale
- 7. Visual Analog Pain Scale
- 8. 10-meter walk test
- 9. NIH stroke scale
- 10. Mini-Mental State Examination
- 11. Geriatric Depression Scale
- 12. Modified Rankin Scale Score
- 13. Grip Strength

Total Score	/66	
Proximal	/36	Subject ID
Wrist/Hand	[ 24	Date
Coordination/Speed	/ 6	Visit #
Affected side (R or L) _	 	

FUGL-MEYER ARM MOTOR ASSESSMENT Remember to score best, not first, patient performance

Pr	oximal				
LF	Reflexes				
Biceps or finger flexor reflex			0 [no reflex]	2 [reflex elicitable]	
2.	Triceps reflex		0 [no reflex]	2 [reflex elicitable]	
Ш	Flexor Synergy				
		cted to voluntarily bring affect lder abducted 90°/externally	ed forearm fully supinated to rotated/retracted/elevated.	ear of the affected side,	
3.	Shoulder girdle retraction	0 [not done at all]	1 [partly done]	2 [faultless]	
4.	Shoulder girdle elevation	0 [not done at all]	1 [partly done]	2 [faultless]	
5.	Shoulder abduction	0 [not done at all]	1 [partly done]	2 [faultless]	

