Stabilization: Examiner manually stabilizes the humerus Goniometer Axis: Over the lateral epicondyle of the humerus

Stationary Arm: Parallel to the longitudinal axis of the humerus pointing towards the tip of the

acromion

Moving Arm: Parallel to the longitudinal axis of the radius pointing towards the styloid process of

the radius

Expected ROM: 0° in males; 10-15° in females is common.

Subject ID:	
Date:	
Fxam#·	

Modified Ashworth Scale of Spasticity

[figure not shown]
After Katz et al, Arch PMR 73:339-347, 1992

Shoulder	Elbow	Wrist	Finger

- 0 No increase in muscle tone.
- Slight increase in tone, manifested by a catch and release or by minimal resistance at the end of the range of motion when the affected part(s) is moved in flexion or extension.
- 1+ Slight increase in muscle tone, manifested by a catch, followed by minimal resistance throughout the remainder (less than half) of the ROM, but affected part(s) easily moved.
- 2 More marked increase in muscle tone through most of the ROM, but affected part(s) easily moved.
- 3 Considerable increase in muscle tone, passive movement difficult.
- 4 Affected part(s) rigid in flexion or extension.

For elbow, go from full flexion to full extension in 1 second with patient supine and arm stop a pad (per Bohannon and Smith, Phys Ther 1987).

Visual Analogue Scales

Subject ID
Date
Visit #
Name of person doing exam

Gait velocity testing - 10m Walk

Record time (to the nearest hundredth of a second) for the subject to complete the 10 meter walk. Record score separately for each of the two trials.

Timed 10meter walk	
Trial #1 (# seconds)	
Trial #2 (# seconds)	

Was an attempt made to evaluate gait velocity testing? Y□or No
If no, enter 999 in both of the above boxes for "# seconds" and state the reason why gait velocity testing could not be attempted:
Was an attempt made to evaluate gait velocity but the subject was not able to initiate even a single step? Your No
If yes, enter 300 in both of the above boxes for "# seconds".
Did subject use any assistive device or orthotic device (e.g., AFO, cane, or walker)? You No
If yes, state the device:
Did study site personnel provide any physical support during gait velocity testing? Y_or No
If yes, describe this support:

1

Exam #:

NIH Stroke Scale--Score first response. No prompting.

TOTAL SCORE

*Indicates option to score X (e.g., joint fusion/amputation); provide explanation.

[figure not shown]
Test	Scale Definition	Score

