stroke. Can assess by grimace or withdrawal if pt	1=Mild-mod sensory loss, less sharp on affected side, pt aware of	
obtunded. Score 2 only if pt clearly comprehends	being touched	
thus aphasics/stupor usually=1.	2=Severe total sensory loss, unaware of touch; unresponsive=2, bilat	
1 1 3	sens loss(brnstem)=2	
9. Best LanguageDescribe cookie thief, name	0=Normal	
pictures, read sentences; can use stereognosis,	1=Mild-mod aphasia	
repetition, or writing. Score=3 only if pt mute &	2=Severe aphasia; great need for guessing & inference by examiner;	
follows no 1 step commands.	lim'd info exchanged. Examiner carries burden of	
	communication.	
	3=Mute, global aphasia, coma	
10. Dysarthria*Have patient read from list of words;	0=Normal	
can rate speech w/severe aphasia. Score=X only if	1=Mild-mod; pt slurs but can be understood	
patient intubated or has other barrier.	2=Severe; unintelligible. Mute/anarthric=2	
11. Extinction & Inattentionsevere vis loss + normal	0=Normal or none detectable	
sens=0; aphasia but attending well bilat'ly=0. Vis	1=Inattention or extinction on DSS in any of vis, auditory, sens,	
neglect or anosognosia =abnl.	spatial, or personal	
	2=Profound in > 1 modality	

Subject ID:
Date:
Exam #
Mini-Mental State Examination CMMSE)
ORIENTATION-onepointforeachanswer
"What is the date to day? (year) (date) (month) (day) (season)?"(5) _ "Where are we? (state) (county) (town) (hospital) (floor)?" (5)
REGISTRATION – score 1,2,3 points according to how many are repeated on first try (Apple, piano, green)
Name three objects: Give the patient one second to say each.
Ask the patient to: repeat all three after you have said them. Repeat them until the patient learns all three. (3)
ATTENTION AND CALCULATION - one point for each correct subtraction
Ask the patient to: begin from 100 and count backwards by 7. Stop after 5 answers. (93, 86, 79, 72, 65) or Spell WORLD backwards (5)
RECALL-onepointforeachcorrectanswer
Ask the patient to: name the three objects from above. (3)
LANGUAGE
Ask the patient to: identify and name a pencil and a watch. (2)
Ask the patient to: repeat the phrase "No ifs, ands, or buts." (1)

Ask the patient to: "Take a paper in your right hand, fold it in half, and put it on the floor
(1 point for each task completed properly)(3)
Ask the patient to: read and obey the following: (1)

Close your eyes

Ask the patient to: write a sentence. (1)	
Ask the patient to: copy a complex diagram of two interlocking pentagons. (1)	

TOTAL:_____/30

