Answers in **bold** and underlined indicate depression. Although differing sensitivities and specificities have been obtained across studies, for clinical purposes a score > 5 points is suggestive of depression and should warrant a follow-up interview. Scores > 10 are almost always depression.

Subject ID:	
Date:	
Exam#:	

Power Grasp Test

	Trial 1	Trial 2	Trial 3	Average
Grasp (kg) Right				
Grasp (kg) Left				

Grasp

- Displays grip force in pounds (0-200) and kilograms (0-90).
- Isometric; accommodates variable size hands, adjusts to five grip positions (1 ¾" to 3 ¾").
- Set adjustable handle to the desired spacing.
- Rotate the peak hold needle counter-clockwise to 0.
- The patient should be seated with shoulder adducted and neutrally rotated, elbow flexed at 90 degrees, and the forearm in neutral position and wrist between 0-30 degrees dorsiflexion and 0-15 degrees ulnar deviation.
- Let the patient comfortably arrange the instrument in hand. Lightly hold around the readout dial to prevent inadvertent dropping
- Have the patient squeeze with maximum strength.
- 3 trials with 2-3 min. rest period between trials.
- The average of the three trials is recorded.
- Compare the other hand and the normative data. Scores within 2 standard deviations of the mean are considered within normal limits.

Subject ID:	
Date:	
Fxam#:	

Pinch Strength Test

Test	Trial 1	Trial 2	Trial 3	Average
Lateral Pinch (kg)				
Right				
Lateral Pinch (kg)				
Left				

Pinch

- Measures key (Lateral Pinch) strength.
- -Measures in pounds (0-45) or kilograms (0-20).
- -ASHT recommends the following test position: patient should be seated, shoulders adducted and neutrally rotated, elbow flexed at 90 degrees, forearm and wrist in neutral position.
- -Key or lateral pinch: pad of thumb and lateral surface of index finger

Daily Procedures:

- 1. Stroke patients admitted to ARU.
- 2. Screen will be done upon admission (within 1-2 days).
- 3. Baseline evaluation will be performed within 1-3 days after the screening visit. The therapist will see patients in a separate room right outside ARU.
- 4. Randomization occurs after baseline evaluation same day if possible. We will use the web-based formula to randomize patients from both study sites.
- 5. Study participants will be assigned to groups the day after randomization and begin their assigned intervention.

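### The severe-tone exclusion requires an Ashworth score above 4, but the printed per-joint grades stop at 4 and no total or recode is defined

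*Combined protocol and SAP*

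**What the plan says.** Exclusion criterion 2, under Inclusion and Exclusion Criteria, reads "Severe tone at the affected upper extremity (score >4 on the Ashworth Spasticity Scale". It refers to the limb as a whole and does not say which joint counts or how several joints combine.

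The Table of Clinical Testing schedules "Modified Ashworth Scale of Spasticity (Shoulder, Elbow, Wrist, Finger" at screening and at all three evaluations. The List of Clinical Tests names the Modified Ashworth and no other version. Its scoring form has one entry per joint and ends with these two grades:

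- "3 Considerable increase in muscle tone, passive movement difficult"
- "4 Affected part(s) rigid in flexion or extension"

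The form also has an intermediate grade without a plain numeric value: "1+ Slight increase in muscle tone, manifested by a catch, followed by minimal resistance throughout the remainder". Its readable text has no total line.

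Two other parts of the document bear on the point. Exclusion criterion 7 is "Inability to perform the experimental task that will be studied". Under Daily Procedures, screening precedes the baseline evaluation, and "Randomization occurs after baseline evaluation same day if possible".

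**The concern.** A numeric exclusion works only if the instrument can return a value beyond the cut-off. Here the cut-off is strictly greater than 4, and 4 is the most severe grade on the form. Taken literally, the one criterion written to keep out severe tone cannot be met.

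The other numeric exclusions do not share the problem. Criterion 3 uses 2 or higher on NIH Stroke Scale question 9. That form prints "2=Severe aphasia; great need for guessing & inference by examiner" and a further grade 3, so 2 of its 4 grades meet the criterion. Criterion 1 uses more than 6 on a 10-point pain scale, which is also reachable.

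What is at stake is the definition of the enrolled population. Staff at two sites must apply the rule to 44 planned participants. Anyone who notices that it cannot be met must guess whether the sign, the number or a missing sum is at fault. Readers of the results would not know what limit on tone was in force.

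**Working it through.** The plan gives no derived figure to reproduce on this point. The check is whether any score on the form satisfies the criterion.

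**Inputs**

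- Threshold: score > 4 (exclusion criterion 2).
- Grades: 0, 1, 1+, 2, 3, 4 (Modified Ashworth form). The numeral for grade 1 is not legible in the available text and is read from its place between 0 and 1+.
- Joints: four (Table of Clinical Testing and the form).
- Value of 1+: not given. Both 1 and 1.5 are tried, as assumptions.

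**Step 1: grades as printed.** Grades above 4: 0 of 6. No single joint can exceed 4, and neither can the maximum or the mean over joints. The worst possible record, 4, 4, 4, 4, has maximum 4 and mean 16/4 = 4, and 4 > 4 is false. This holds for either value of 1+.

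**Step 2: readings the document does not define.** These are assumptions, used only to see whether an obvious intended meaning would settle the matter. There are 6^4 = 1,296 possible four-joint records. The counts below are of possible records, not patients, and say nothing about how often each occurs.

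| Reading | Range | Records meeting > 4 |
|---|---|---|
| Any joint, printed grades | 0 to 4 | 0 |
| Any joint, grades recoded 0 to 5 | 0 to 5 | 1,296 − 5^4 = 671 |
| Four-joint sum, 1+ = 1 | 0 to 16 | 1,101 |
| Four-joint sum, 1+ = 1.5 | 0 to 16 | 1,168 |
| Four-joint sum of recoded grades | 0 to 20 | 1,226 |

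- *Recode by joint.* Mapping 0, 1, 1+, 2, 3, 4 to 0, 1, 2, 3, 4, 5 leaves only printed grade 4 (recoded 5) above 4.
- *Sum with 1+ = 1.* Records totalling 0, 1, 2, 3 and 4 number 1, 8, 28, 60 and 98, which is 195 in all; 1,296 − 195 = 1,101.
- *Sum of recoded grades.* Records totalling 4 or less number C(8,4) = 70; 1,296 − 70 = 1,226.

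**Step 3: do the reachable readings agree?** They do not.

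- Grades 1, 1, 1, 2 sum to 5 and are excluded by the sum, but not by the recode by joint.
- Grades 4, 0, 0, 0 sum to 4 and are not excluded by the plain sum, but are excluded by the recode by joint, where the rigid joint scores 5.
- Under the plain sum, 1+ at all four joints totals 4 (not excluded) if 1+ = 1, and 6 (excluded) if 1+ = 1.5.

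So the criterion runs from excluding nobody to excluding low grades spread over several joints, depending on a rule that the readable text does not state.

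**The case against.** The strongest counter-argument is that this is an undefined scoring unit rather than a contradiction. The criterion speaks of the whole upper extremity while the form records four joints, and a limb-level total could exceed 4. That is possible but unsupported. The Fugl-Meyer, Action Research Arm Test and Mini-Mental State forms all print a total; the readable Ashworth form does not. Statistical Considerations names Ashworth as an outcome without any scoring rule.

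Second, one figure on the Ashworth form is not reproduced in the available text, so a scoring key inside it cannot be ruled out. This caveat stands. The grade descriptions and joint entries are legible apart from the numeral 1, and no readable text points to such a key.

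Third, the criterion omits the word Modified. Treating it as the Modified Ashworth is an inference, but the document offers no other version and this is the one scheduled at screening.

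Fourth, the practical effect may be small. The criterion says in words that severe tone is meant. Exclusion 7 may remove patients whose rigid arm cannot do the task, and exclusion 1 removes those with pain above its own cut-off. This also stands in part: these rules limit the consequence, but neither sets a tone threshold or makes the number in criterion 2 usable. Nothing in the document shows that the two sites in fact screened differently.

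**Conclusion.** The criterion is wrong as written. Against the only Ashworth form in the document, 0 of 6 grades exceed 4, and a patient rigid at every joint is not excluded for severe tone. The conclusion rests on three assumptions: the criterion refers to the Modified Ashworth, scores are taken by joint as the form is laid out, and the figure not reproduced holds no scoring rule.

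The consequence is limited to eligibility. The rule is applied before allocation, so it does not by itself bias the comparison between groups, and no effect on the planned 44 participants or the primary Fugl-Meyer analysis is shown. The document gives nothing from which to estimate how many patients are affected. It should be corrected because it is a decision figure that cannot operate, not because it threatens the main result.

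**What to change.** The sponsor should reconcile exclusion criterion 2 with the Modified Ashworth form in one of two ways:

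- restate the criterion so that it can be reached on the printed grades, and name the joint or joints to which it applies; or
- if a sum or recode was intended, define it in the criterion and on the form, including the numeric value of 1+.

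The criterion should name the scale in the same words as the form and be applied in the same way at both sites before randomisation. If the figure on the form already holds a scoring rule, the criterion should refer to it. Which cut-off is right is for the sponsor to decide; none is proposed here.

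The cost is a one-line amendment, plus a line on the form if a sum or recode is used. The assessment is already done at screening, so no visit or test is added. The downside is that a working threshold may exclude some patients who would now pass and so slow accrual, by an amount the document does not allow one to estimate.

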- "If you pick up two blocks at a time, they will count as one. If you drop one on the floor or table after you have carried it across, it will still be counted, so do not waste time picking it up. If you toss the blocks without your fingers crossing the partition, they will not be counted. Before you start, you will have a chance to practice for 15 seconds. Do you have any questions? Place your hands on the sides of the box. When it is time to start, I will say 'READY' and then 'GO."
- Perform a 15 second practice. If mistakes are made, correct them.
- "This will be the actual test. The instructions are the same. Work as quickly as you can. READY... (wait 3 seconds) GO."
- After one-minute STOP
- Count the number of blocks transported and record. Subtract blocks transported more than one at a time or if the fingertips did not cross over
- Turn the box so all the blocks are on the same side as the next hand to be tested
- "Now you are to do the same thing with your left hand. First you can practice. Put your hands on the sides of the box as before. Pick up one block at a time with your hand and drop it on the other side of the box. READY... (wait 3 seconds) GO."

MOTOR ACTIVITY LOG

	Task	Use?	AS	HW	If no, why?
1.	Turn on light switch				
2.	Open drawer				
3.	Remove clothing from drawer				
4.	Pick up phone				
5.	Wipe off counter				
6.	Get out of car				
7.	Open refrigerator				
8.	Open door with doorknob				
9.	Use TV remote				
10.	Wash your hands				
11.	Turn on/off water faucet				
12.	Dry your hands				
13.	Put on socks				
14.	Take off socks				
15.	Put on shoes				
16.	Take off shoes				
17.	Get up from chair with armrests				
18.	Pull chair away from table				
19.	Pull chair towards table				
20.	Pick up glass/bottle/cup/can				
21.	Brush your teeth				
22.	Put makeup/lotion/cream on face				
23.	Use key to unlock door				
24.	Write on paper				
25.	Carry object in hand				
26.	Use fork or spoon				
27.	Comb your hair				
28.	Pick up cup by handle				
29.	Button a shirt				
30.	Eat half sandwich or finger food				
	MEAN SCORE				

	20.	rick up cup by numaic				
	29.	Button a shirt				
	30.	Eat half sandwich or finger food				
		MEAN SCORE				
L. 2.		perform this activity during the past week? Yes or ich did your affected arm participate in this activit			Subject ID:	
3.	•	7/ Not at All) 5 (Always During/ Il did your affected arm help during this activity? (•	f Movement)	Date:	

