- 9. If supervising therapists at ARU and research therapist believe LARA participants are skilled enough to drive LARA, participants will begin using LARA to go to therapy appointments and move around ARU by themselves.
- 10. 3 clinical evaluations: baseline, 3-week post therapy or the day before discharge if sooner, 3-month follow up. All clinical evaluations must be completed within 2 days of scheduled dates.
- 11. 3-month follow up is 3 months after baseline evaluation.

Statistical Considerations

Data will be analyzed using modified intention-to-treat analysis. That is, all participants will be included in the analysis if data from the last follow-up assessment is available, regardless of treatment they receive or deviations from protocol. For missing data, we will carry forward the last available value. The effect of treatment on each outcome measure will be assessed using a repeated-measures ANOVA. Follow up analysis will be done using t-tests with Bonferroni corrections, or Wilcoxon rank sum tests if the distributions fail the Lilliefors test for normality. We hypothesize that the participants in the LARA therapy group will have significantly greater reductions in motor impairment measured by FM score than participants in the conventional therapy group. We expect this will be due to the increased dose of therapy LARA provides, and we will include total arm activity (as measured by the wrist-mounted actigraphy) and baseline function as covariates in the analysis. We will compare changes in MAL score, ARAT score, range of motion at the shoulder and elbow, Visual Analog Pain scores, Ashworth Spasticity, and 10 min walk scores using student's t-test or Wilcoxon rank sum tests for non-parametric data. We expect improvements in functional use of the impaired limb (MAL and ARAT) and range of motion but expect no significant differences in pain, spasticity, wheelchair odometer reading, or walking speed. All analyses will be reviewed by our statistical consultant.

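### For the earliest participants the baseline Motor Activity Log looks back past the stroke; this adds noise to the tested change in MAL but does not bias the group comparison

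*Combined protocol and SAP*

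**What the plan says.** - **Recall period.** The MAL form (List of Clinical Tests) asks of each of 30 activities whether the patient did "perform this activity during the past week" (yes or no), then how much and how well the affected arm took part, on 0-5 scales. The top of the how-well scale is use equal to that before the stroke. No legible instruction on the form limits recall to days since the stroke.
- **Entry.** The first inclusion criterion is "History of stroke affecting the arm, at least 3 days to 30 days prior to enrollment".
- **Baseline timing.** Daily Procedures item 3: "Baseline evaluation will be performed within 1-3 days after the screening visit". Item 2 places screening shortly after admission to the rehabilitation unit, so baseline is planned in inpatients. Item 4 places randomization after baseline.
- **Schedule.** The Table of Clinical Testing marks the MAL at baseline, post therapy and 3-month follow-up.
- **Analysis.** Statistical Considerations: "We will compare changes in MAL score, ARAT score, range of motion at the shoulder and elbow", along with other measures, by Student's t-test or Wilcoxon rank sum test. The same section names MAL and ARAT as the measures on which improved functional use of the impaired limb is expected.

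**The concern.** A seven-day recall taken four to six days after the stroke covers days on which the arm was normal. A participant who answers the question as printed can credit some of that use to the arm that is now weak. Baseline MAL is then too high, and that participant's change too small by the same amount. A t-test or rank test on raw change passes the whole baseline error into the result.

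A second feature works in the opposite direction. Some items, such as getting out of a car or unlocking a door with a key, are hard to attempt on an inpatient unit but ordinary at home. Baseline can be low for lack of opportunity, so change to three months partly reflects going home.

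At stake are the precision of one functional-use comparison in a trial of 44 and the reading of MAL change as recovery.

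**Working it through.** The documents give no SD, effect size or power for the MAL and no derivation of the 44, so there is no planned figure to reproduce. The check is date arithmetic, followed by a sizing on stated assumptions.

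**1. Pre-stroke days in the recall window.** Take enrolment as the screening visit. Baseline day = screening day + gap (1, 2 or 3). Pre-stroke days = max(0, 7 − baseline day).

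| Screening day | Gap 1 | Gap 2 | Gap 3 |
|---|---|---|---|
| 3 | day 4: 3/7 | day 5: 2/7 | day 6: 1/7 |
| 4 | day 5: 2/7 | day 6: 1/7 | day 7: 0 |
| 5 | day 6: 1/7 | day 7: 0 | day 8: 0 |
| 6 or later | 0 | 0 | 0 |

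Six combinations are affected. If enrolment instead means the baseline visit, day 3 is possible and the overlap is 4 of 7 days.

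**2. Share affected** (assumption: gap uniform over 1-3 days).
- Screening uniform over days 3-30: 28 × 3 = 84 combinations; 6/84 = 7.1%; 0.071 × 44 ≈ 3 participants.
- Screening uniform over days 3-10: 8 × 3 = 24 combinations; 6/24 = 25%; 11 participants.

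**3. Size of the over-report** (assumptions: post-stroke MAL 0.8, pre-stroke use scored 5, weighted by days). Over-report = share × (5 − 0.8) = 4.2 × share, which is 1.8, 1.2 and 0.6 points for baselines on days 4, 5 and 6.
- Mean share over the six combinations: (3+2+1+2+1+1)/(6 × 7) = 10/42 = 0.238. Mean over-report: 4.2 × 0.238 = 1.0 point.
- Mean square: (1.8² + 2 × 1.2² + 3 × 0.6²)/6 = 7.2/6 = 1.2.

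**4. Effect on mean change.** Share affected × 1.0 = 0.07 points at 7.1% and 0.25 points at 25%.

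**5. Effect on variance of change.** Added variance = p × 1.2 − (p × 1.0)².
- p = 0.071: 0.0857 − 0.0051 = 0.081.
- p = 0.25: 0.300 − 0.0625 = 0.2375.
- With an assumed SD of change of 1.3 (variance 1.69): 0.081/1.69 = 4.8% and 0.2375/1.69 = 14.1%. Equivalent sample: 44/1.048 = 42 and 44/1.141 = 39.
- The percentage depends on the assumed SD. At 0.9 (variance 0.81) the same added variance is 10% and 29%.

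**6. Group comparison.** A simulation used 22 per arm (assumed; no ratio is stated), mean baseline about 0.8, control gain 1.2 with SD 0.9, and a true group difference of 0.8.

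| Screening days | Observed control gain | Observed difference | SD of change | Power |
|---|---|---|---|---|
| No contamination | 1.20 | 0.80 | 0.90 | 82% |
| 3-30 | 1.13 | 0.80 | 0.94 | 79% |
| 3-14 | 1.04 | 0.80 | 0.99 | 74% |
| 3-10 | 0.95 | 0.80 | 1.02 | 71% |

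With no true difference, the rejection rate stayed at about 5% throughout.

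**7. Chance imbalance.** With three affected participants and 22 per arm, all three fall in one arm with probability 2 × C(22,3)/C(44,3) = 3,080/13,244 = 23%. At 1.0 point each, the group difference then moves by 3 × 1.0/22 = 0.14 points.

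**The case against.** The strongest reply is that randomization protects the comparison. Baseline is taken before allocation, so inflated baselines and the move from hospital to home are balanced between arms in expectation. A lopsided split is ordinary chance imbalance, which the test's error rate already covers. This stands. A reader might infer that the planned MAL comparison is biased for or against LARA; the documents do not support that, and the simulation shows an unbiased difference.

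The form also gives some protection. It asks about the affected arm and uses the pre-stroke state as its reference, a therapist sees patients at baseline, and severe aphasia and interfering cognitive deficits are excluded. Many patients may answer for the time since the stroke unprompted. This is a reason to treat the sizes above as what happens if the printed question is answered literally, but nothing on the form restricts the window.

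A reader might also infer a drastic loss of information. Day-weighting does not allow it: even with no use at all after the stroke, the most a day-4 baseline can gain is 3/7 × 5 = 2.1 points, and most affected baselines gain less. The 25% share needs all screening to fall in days 3-10, which the plan does not state.

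The two errors run in opposite directions, so the net sign of the error in mean change is unknown. That argues against any claim about direction, but it does not make within-group change easier to interpret.

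Finally, the MAL is not among the secondary outcomes listed under Methods, and Statistical Considerations also applies a repeated-measures ANOVA to each outcome measure, so the change-score test is not the only MAL analysis. Both points limit the importance. The ANOVA, however, uses the same baseline.

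**Conclusion.** The concern holds in a limited form. As printed, the recall period gives a baseline that can include pre-stroke arm use for participants evaluated on days 4-6. The effect on the planned group comparison is lost precision and chance imbalance, not bias. Within-group MAL change cannot be read cleanly as recovery, because of the recall overlap in a few participants and the change of setting more generally.

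On the assumptions in the working, the overlap affects about 3 of 44 participants, rising to 11 of 44 only if screening is concentrated in days 3-10. Mean change is understated by about 0.07-0.25 points and its variance rises by about 5-14%; a smaller true SD would make the percentage larger. The share of early baselines, the MAL levels and the SD are all assumed, since the documents give none of them.

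The primary Fugl-Meyer analysis is untouched. The point is worth acting on because the error is built into a printed question and costs almost nothing to remove.

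**What to change.** 1. **Form.** At Evaluation 1, word the MAL question to cover the time since the stroke whenever the stroke was less than 7 days earlier. The window becomes 4, 5 or 6 days for baselines on days 4, 5 or 6, with no pre-stroke overlap. Nothing changes from day 7 onward.
2. **Analysis.** In Statistical Considerations, replace the t-test or Wilcoxon test on raw MAL change with a between-group comparison of MAL at Evaluation 3, adjusted for one measure of baseline function named in advance (ARAT or Fugl-Meyer). Report MAL change descriptively. Both covariates are already collected at baseline, and the section already foresees baseline function as a covariate.

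The cost is one line on the form and one sentence in the analysis section, with no added visits or participants. The recall window is shorter for the earliest participants, and MAL change is no longer the tested quantity.

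Leaving items with no opportunity out of the mean is not part of this recommendation. It would give different item sets by visit and participant, which is a debatable scoring choice, and the form already has a column for the reason an activity was not done.
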